6.1 Sample Size Determination

Sample size determination was based on obtaining a reasonable amount of subjects to have meaningful results that will allow completion of the study in time allotted.

6.2 Statistical Methods

Demographics and other baseline characteristics will be presented by means of descriptive statistics.

The primary objective is to compare differences in margin exposure of the abutment between baseline to 6 months later. The null hypothesis is that there is no difference in the margin exposure of the abutment between those 2 visits. Ho will be tested by means of Fisher's exact test, after each abutment margin is classified as it shows or not. A p-value less than 5% will be regarded statistically significant.

Secondary objectives include:

Measurement of the soft tissue response based on the condition of the peri-implant mucosa (bleeding on probing). Fisher's exact test will be used after the site has been evaluated for presence of bleeding or not. Provisional crown fit at delivery of provisional crown- Fisher's exact test will be used after the provisional crown is determined to fit or not.

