1.2 Clinical Data to Date

There is no available clinical data that pertains to this study in which this protocol developed by Astra-Tech is used to fabricate custom Atlantis abutments prior to guided surgery.

2 Study Objectives

Purpose: To evaluate the possibility of fabricating an ideal CAD/CAM custom abutment that adequately supports the hard and soft tissues in a single edentulous space prior to guided surgery. Evaluation of the custom abutment will be completed at 2 intervals post operatively, with abutment exposure being the primary outcome at follow-up. With knowledge of fabricating the definitive CAD/CAM abutment prior to surgery, soft tissue development can begin immediately and restoration of the implant can be completed without subsequent soft tissue trauma during crown fabrication.

Participants: The study will seek 24 patients with a minimum of 20 teeth who have a bound edentulous space who seek restoration with a dental implant crown.

Procedures (methods): This is a convenience sample, we will recruit subjects who present to the graduate prosthodontics clinic or inquire about the study will be eligible to receive dental implant surgery with subsequent definitive abutment and provisional crown delivery at eight weeks. The group will then be randomly split with half of the group receiving a custom abutment with margin placement .5mm sub-gingivally and half of the group receiving a custom abutment with margin placement 1.5 mm sub-gingivally. Final impression for the definitive e-max all-ceramic crown will be completed at eight weeks with final crown delivery at eleven weeks. Follow-up and data collection will be completed at eight weeks, eleven weeks, and twenty-four weeks post operatively.

Primary Objective

Abutment margin exposure

Secondary Objective

Provisional crown fit.

3 Study Design

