3.1 General Design

The general design of the study is a cohort study with 2 arms in which subjects are randomly assigned to one of 2 experimental groups. The expected duration of subject participation is 7 months. The subjects will complete 7 appointments within this 7 months span that includes initial screening, CBCT evaluation of the site, surgical placement of the dental implant, restoration of the dental implant and associated follow-ups at 7 days, 8 weeks, 11 weeks and 24 weeks.

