3.2 Primary Study Endpoints

The primary objective is to compare differences in margin exposure of the abutment between baseline to 6 months later.

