5.1 Visit 1 (1 hour)

Appointment 1: Screening Exam (1 hour), Prior to inclusion into study

All patients will receive standard care for their initial clinical appointment. This appointment is not research-driven. Standard care includes:

- General extraoral and intraoral exam
- Maxillary and mandibular alginate impressions
- Standardized radiographs (panoramic film)
- Standardized photographs
- Completion of the dental implant surgery consent form
- Completion of the treatment in the graduate Prosthodontic clinic consent form

If the patient is eligible for the research study, s/he will be introduced to the study and given a copy of the consent form to take home. If the potential subject is interested in participating in the study, the consent form will be signed at the beginning of visit 2 and the subject will be enrolled.

5.2 Visit 2

Appointment 2: Completion of consent for inclusion into study, CBCT with scanning appliance

CBCT will be obtained of surgical site to be used for planning and surgical guide fabrication. This procedure is the standard of care for implant patients within the school of dentistry.

5.3 Visit 3

Appointment 3: Place implant in healed alveolar ridge

Each patient will have the opportunity to ask remaining questions about the surgery protocol. Each patient will use a pre-operative rinse of antibacterial mouth rinse (Peridex).

Standard UNC Graduate Prosthodontics clinic protocol for implant placement will be used including full body sterile drape of patient as well as surgical scrub of both operator and assistant. Local anesthetic will be used at

surgical site (2% lidocaine 1:100,000 Epinephrine).

An Astra Tech dental implant will be placed using standard clinical protocol. The dental implant will be covered with a cover screw to allow soft tissue healing. A post-operative radiograph will be made to demonstrate proper placement of the implant in bone.

The patient will be prescribed normal post-operative medications including analgesics and anti-bacterial mouth rinse (peridex). All procedures listed are the standard of care for implant placement.

5.4 Visit 4

Appointment 4: Follow-up (1 week post-op)

Usual and customary follow-up to be completed to verify adequate and acceptable healing of surgical site. This procedure is the standard of care for implant placement.

5.5 Visit 5

Appointment 5: Final impression (8 weeks post-op) for full coverage crown

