Final impression for crown fabrication of the abutment will be completed at 8 weeks post surgery using standard clinical protocol. Provisional restorations will be placed onto final abutments delivered at same appointment. These procedures are standard of care for all participants. Research-driven data to include abutment exposure will be collected from subjects regarding fit of the provisional restoration. A peri-apical radiograph of the implant in bone is produced to demonstrate the proper connection of the abutment to the implant at the time of placement of the abutment.

5.6 Visit 6

Appointment 6: Delivery final E-max crown restoration (11 weeks post-op)

Delivery of final crown will be completed using standard clinical protocol at 11 weeks post-surgery. Research driven data to include abutment exposure will be collected from all subjects regarding esthetics of the final abutment.

5.7 Visit 7

Appointment 7: Follow-up 24 weeks post-op

Follow-up of crown restorations will be completed at 6 months post surgery (24 weeks). Research driven data to include abutment exposure will be collected for all subjects. Bleeding on probing measurements will be made to evaluate soft tissue health around the abutments (Standard of Care). A peri-apical radiograph will be made for hard tissue evaluation of the abutment (Standard of Care). Photographs will be taken of restorations per standard protocol (photographs are standard of care). The patient will then be dismissed from the study.

6 Statistical Plan

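### The trial randomises abutment margin depth, but its primary hypothesis compares two visits and no between-arm comparison of margin exposure is specified

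*Combined protocol and SAP*

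**What the plan says.** Section 2 (Study Objectives) splits the sample at random, half receiving "margin placement .5mm sub-gingivally and half of the group receiving a custom abutment with margin placement 1.5 mm sub-gingivally". Section 3.1 confirms that "subjects are randomly assigned to one of 2 experimental groups". Margin depth is the only thing assigned by randomisation.

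Section 3.2 defines the primary endpoint over time: "The primary objective is to compare differences in margin exposure of the abutment between baseline to 6 months later". Section 6.2 repeats this and adds: "The null hypothesis is that there is no difference in the margin exposure of the abutment between those 2 visits". The test is Fisher's exact test at the 5% level, with each margin classed as showing or not.

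Fisher's test is also named for bleeding on probing and for provisional crown fit, with no grouping factor given for either. The Study Summary names the test and nothing more. Section 6.3 says who is analysed (all randomised subjects) but not what is compared.

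On timing, section 5.3 says of the surgical visit: "The dental implant will be covered with a cover screw to allow soft tissue healing". Section 5.5 says of week 8: "Provisional restorations will be placed onto final abutments delivered at same appointment". Section 5.7 says of week 24: "Research driven data to include abutment exposure will be collected for all subjects". No section says which visit is baseline.

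**The concern.** Depth is fixed within a subject. A comparison of two visits therefore reflects healing time and the change from provisional to final crown, averaged over the two depths and without a control. It cannot isolate an effect of depth, which is the only contrast that the randomisation supports.

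Week-24 exposure is recorded for everyone, so a table by arm could be made afterwards, but it would be post hoc. Whether to analyse week-24 status or new exposure since week 8 would then be decided with the data in view, and the two can give different answers.

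Two further faults follow from the same sentence. Read literally, it applies a test for independent groups to two readings on the same subjects. It also relies on a baseline that is never defined.

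**Working it through.** **Inputs from the documents.** N = 24, split in half, so 12 per arm (section 2). Binary outcome, Fisher's exact test, 5% level (section 6.2). Sidedness is not stated; I take two-sided. Section 6.1 gives no rate, effect size or power, so there is no planned figure to reproduce. Every count and rate below is an assumption.

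**When exposure can first be read.** The implant is under a cover screw after surgery (5.3) and the abutment is delivered at week 8 (5.5). Week 8 is therefore the earliest possible reading. Baseline to 6 months is then 24 − 8 = 16 weeks, and the assigned depth is already in place at that baseline.

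**1. Same primary result, opposite arm results.** Assume 0/24 exposed at baseline and 6/24 at week 24. When one margin is zero and the groups are equal, two-sided Fisher p is twice the single-tail probability.

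- Visits: 2 × C(24,6)/C(48,6) = 2 × 134,596/12,271,512 = 0.022.
- Arms, 6/12 v 0/12: 2 × C(12,6)/C(24,6) = 2 × 924/134,596 = 0.014. Risk difference 50 points, Newcombe 95% CI 15.4 to 74.6.
- Arms, 3/12 v 3/12: p = 1.0. Difference 0 points, CI −32.5 to 32.5.

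The visit p-value is 0.022 in both cases.

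**2. Over repeated trials.** Assume none exposed at baseline and independent binomial counts at week 24, n = 12 per arm. The visit test is significant when the total exposed is at least 5 (0/24 v 5/24 gives p = 0.0496). Enumerating all outcomes:

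| Week-24 rates | Visit test significant | Arm test significant |
|---|---|---|
| 25% v 25% | 75% | 1.5% |
| 45% v 5% | 79% | 48% |

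The 75% is not a false-positive rate. Exposure does rise from 0% to 25% in that row, so it is the power of the visit test for its own question. The point is that the visit test hardly moves (75% to 79%) when a 40-point depth effect is introduced.

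**3. The choice of arm endpoint matters.** Assume week 8 at 2/12 v 0/12, week 24 at 6/12 v 0/12, and no reversals.

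| Analysis | Data | p |
|---|---|---|
| Visit, Fisher | 2/24 v 6/24 | 0.245 |
| Visit, exact McNemar | 4 new, 0 reversed: 2 × 0.5⁴ | 0.125 |
| Arms, new exposure | 4/12 v 0/12 | 0.093 |
| Arms, week-24 status | 6/12 v 0/12 | 0.014 |

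Four defensible readings of one data set run from 0.245 to 0.014.

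**4. Ignoring the pairing.** With no reversals, exact McNemar p = 2 × 0.5^k for k new exposures.

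- 0/24 to 5/24: Fisher 0.0496, McNemar 2 × 0.5⁵ = 0.0625.
- 12/24 to 18/24: Fisher 0.135, McNemar 2 × 0.5⁶ = 0.031.

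The error can go in either direction.

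**5. What the arm comparison can deliver at 12 per arm.** Against 0/12, Fisher first falls below 0.05 at 5/12 (p = 0.037; 42 points, CI 8.7 to 68.0). 5/12 v 1/12 gives p = 0.155 (33 points, CI −1.8 to 60.6). Exact power for 60%, 50%, 40% and 20% against 5% is 78%, 59%, 36% and 4%.

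**The case against.** The best defence is that an arm comparison was meant and badly worded. Fisher's test is for independent groups. Bleeding is scheduled only at week 24 and crown fit is judged only at provisional delivery, so arm is the only grouping available for both secondary tests. The primary endpoint could then be read as change compared between arms. That reading is plausible, but the null hypothesis names visits and no section names the arms in connection with exposure. If arms were meant, the hypothesis is misstated. If visits were meant, the test is the wrong one for paired data. Section 6.2 needs correcting either way.

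Second, this is a pilot with a feasibility purpose: "To evaluate the possibility of fabricating an ideal CAD/CAM custom abutment that adequately supports the hard and soft tissues". Whether margins become exposed by 24 weeks bears directly on that, so the visit question is legitimate and may stay primary. This stands, and it is why changing the primary hypothesis is a recommendation only. It does not excuse leaving the randomised contrast unspecified in a plan that sets a significance threshold.

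Third, a sponsor could prefer new exposure after delivery, because section 1.1 allows that guide error may affect how the abutment sits from the start. That is a fair interest, and new exposure should be shown by arm. However, week-8 exposure is read with the assigned depth already in place, so change from week 8 discards any depth effect present at delivery.

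Fourth, 12 per arm gives a weak test. This is true, and it is a reason to lead with an estimate and its interval.

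**Conclusion.** The concern holds and must be fixed. The plan randomises depth and states no between-arm hypothesis, estimate or test of exposure. Its primary analysis as written returns the same p-value (0.022 under the assumed 0/24 and 6/24) for a 50-point difference between depths and for none. It also ignores the pairing of visits and leaves baseline undefined.

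The textual finding does not depend on any assumed rate. The sizes do: all exposure rates, the two-sided level and full follow-up of 12 per arm are assumptions. That an arm comparison was intended remains possible, but the text does not say so.

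**What to change.** **Essential.** In sections 3.2 and 6.2:

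- Prespecify the between-arm comparison of the proportion of abutments with an exposed margin at 24 weeks, analysed as randomised. Report the risk difference with a 95% CI as the main result and Fisher's exact test beside it.
- Tabulate exposure by arm at 8, 11 and 24 weeks.
- Define baseline as the first abutment assessment, at week 8.
- Analyse any visit comparison as within-subject change with an exact McNemar test, and show new exposure since week 8 by arm.
- State that the bleeding and crown-fit tests compare arms.
- Describe the result as a pilot estimate, and say that p > 0.05 is not evidence that the two depths are equivalent.

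**Recommended.** Make the week-24 arm comparison the primary hypothesis and move the visit question to secondary. If the sponsor keeps the visit question as primary, the essential items still apply.

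**Cost.** Rewording of two sections, one 2×2 table with an interval and one by-arm visit table. No new data, visits or patients. The downside is wide intervals and low power at 12 per arm, which the report should state plainly.

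### The only primary inference in 6.2 is a test of no change in margin exposure, and a non-significant result cannot show that margins stay covered: 4 of 24 newly exposed would still give p=0.109

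*Combined protocol and SAP*

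**What the plan says.** Section 2 gives the purpose: "To evaluate the possibility of fabricating an ideal CAD/CAM custom abutment that adequately supports the hard and soft tissues". It names abutment exposure as the primary outcome at follow-up. All subjects receive the pre-made custom abutment. Randomisation is between two margin depths, 0.5 mm and 1.5 mm below the gingiva, half the group to each, so there is no conventional-abutment control.

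Section 6.2 sets the primary objective as to "compare differences in margin exposure of the abutment between baseline to 6 months later". The hypothesis is: "The null hypothesis is that there is no difference in the margin exposure of the abutment between those 2 visits". The method is: "Ho will be tested by means of Fisher's exact test, after each abutment margin is classified as it shows or not". The decision rule is: "A p-value less than 5% will be regarded statistically significant".

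Section 6.1 justifies the 24 subjects by "a reasonable amount of subjects to have meaningful results" and by the time available. Neither section gives an expected or acceptable exposure rate, a margin, a confidence interval, a power figure, or a statement of how a non-significant result will be interpreted.

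**The concern.** If the abutment supports the tissues, its margin stays covered. New exposure would count against it. The result that agrees with the purpose is therefore little or no exposure, which under 6.2 would appear as a failure to reject the null hypothesis. Failure to reject shows only that the data did not establish a change. It becomes more likely as fewer subjects are observed, so drop-out makes it easier to obtain.

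A test of change between visits also says nothing about the level of exposure. A margin that shows at both visits contributes no change, although it is a failure of the abutment on the trial's own primary outcome.

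At stake is the main conclusion. A report of no significant difference in exposure could be taken as support for the method when the data are compatible with a high exposure rate.

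**Working it through.** **Inputs.** From the documents: 24 subjects (sections 2 and 6.1), half to each depth, hence 12 per arm (section 2); Fisher's exact test on shows or does not show, threshold 5% (6.2). Section 6.1 contains no power calculation, so there is no figure of the plan's own to reproduce.

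Assumptions, because the documents do not say: the test is two-sided; the first reading is at week 8, when the abutment is delivered (5.5), and the second at week 24 (5.7); all 24 are followed; no margin shows at the first reading. The last is plausible because margins are planned below the gingiva. It is varied in step 3.

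**Step 1. Smallest significant result, Fisher as written, 24 v 24 readings.** With 0 exposed at the first reading and k at the second, the two-sided p-value is 2 × C(24,k) / C(48,k).

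- k=4: 2 × 10,626 / 194,580 = 0.109, not significant.
- k=5: 2 × 42,504 / 1,712,304 = 0.0496, just significant.

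So up to 4/24 = 16.7% newly exposed margins are non-significant. The exact (Clopper-Pearson) two-sided 95% interval for 4/24 is 4.7 to 37.4%.

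**Step 2. Chance of a non-significant result.** With no exposure at the first reading this is P(X ≤ 4) for X ~ Binomial(24, rate).

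| True new-exposure rate | 10% | 15% | 20% | 25% | 30% |
|---|---|---|---|---|---|
| Non-significant | 91% | 71% | 46% | 25% | 11% |

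The chance passes 50% at a true rate of about 19%. Below that a miss is more likely than not; above it, detection is more likely. Power reaches 80% at about 26%.

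**Step 3. Some margins already showing at the first reading.** With 1/24 at first, 6/24 later gives p=0.097 and 7/24 is needed. With 2/24 at first, 8/24 gives p=0.072 and 9/24 is needed. Treating the two sets of readings as independent, as the planned test does, the chance of non-significance at a true 20% second-visit rate rises from 46% to 76% if the first-visit rate is 5%, and to 90% if it is 10%. At a true 25% it rises from 25% to 60% and 81%.

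**Step 4. Exposure at both visits.** 12/24 at each visit gives p=1.0, with half the margins showing throughout.

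**Step 5. Would a paired test cure this?** No. The readings come from the same subjects, and exact McNemar with k one-way changes has p = 2 × 0.5^k. That is 0.0625 for 5 and 0.031 for 6, so one more exposed margin would be needed.

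**Step 6. What estimation at week 24 can show.** With no exposures the one-sided exact 95% upper limit is 1 − 0.05^(1/n): 11.7% for n=24 and 22.1% for n=12.

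| Exposed | One-sided 95% upper limit | Upper end of two-sided 95% interval |
|---|---|---|
| 0/24 | 11.7% | 14.2% |
| 1/24 | 18.3% | 21.1% |
| 2/24 | 24.0% | 27.0% |
| 3/24 | 29.2% | 32.4% |

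**The case against.** The strongest reply is that the plan never says a non-significant result will count as success. Section 2 speaks of evaluating a possibility, the title calls the trial a pilot, and 6.2 defines only when a result is significant. A reader might infer that p≥5% is the planned criterion for a favourable conclusion and that the burden of proof has been reversed by design. The documents do not support that; they leave the interpretation open. This stands. What remains is that the plan offers no other basis for a primary conclusion and nothing to prevent the misreading.

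A reader might also infer that a substantial exposure rate would probably be missed. The documents define no important rate, so none can be called substantial from them. With no first-visit exposure, the planned test more often detects than misses a true 20% rate, and it misses 25% only a quarter of the time. Figures from a paired test or an assumed drop-out rate would look worse, but the plan names Fisher's test and gives no drop-out rate.

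A third objection is that pooling all 24 subjects mixes two randomised depths whose exposure risks may differ. This stands too, and the fix has to report each arm.

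Pilot status does not answer the core point. Section 6.2 sets a null hypothesis and a significance threshold, and a pilot of this size is better served by estimation.

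**Conclusion.** The concern holds in limited form. The planned primary test cannot positively support the purpose in section 2, because non-rejection does not show that margins stay covered and a test of change ignores exposure present throughout. With no exposure at the first reading, complete follow-up and a two-sided 5% level, as many as 4 of 24 newly exposed margins would be non-significant, with data compatible with a true rate of up to 37%. The chance of non-significance depends strongly on the first-visit rate, which the documents do not give, so no single probability of missing a problem can be stated.

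This is a gap in the basis for interpretation, not a stated rule that non-significance equals success. It is a worthwhile, inexpensive improvement rather than a defect that must be cured before the trial can proceed.

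**What to change.** In 6.2:

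1. Make the primary result the proportion of margins exposed at week 24 with an exact (Clopper-Pearson) 95% interval, overall and separately for the 0.5 mm and 1.5 mm arms.
2. Base any statement about adequate support on the upper limit, and say in advance whether that is the one-sided 95% limit or the upper end of the two-sided interval, since they differ (11.7% and 14.2% for 0/24).
3. State that p≥5% is not evidence that margins stay covered.
4. State what the sample can show: one-sided 95% upper limits of 11.7, 18.3, 24.0 and 29.2% for 0, 1, 2 and 3 of 24, and about 22% for 0/12 within an arm. Note that the pooled figures describe a mixture of the two depths.

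A ceiling for acceptable exposure is optional. The documents give no basis for choosing one; if the investigators want it, they should fix it before the first subject is enrolled.

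The cost is wording only. Exposure is already recorded at week 24 (5.7), so no subjects, visits or measurements are added. The downside is a less favourable claim: even 0/24 exposed supports only a rate below about 12% for the two depths pooled, and 0/12 only a rate below about 22% for one depth.

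### The primary null compares two visits, but the named test, Fisher's exact test, is for independent groups: null and test do not match

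*Combined protocol and SAP*

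**What the plan says.** Section 6.2 (Statistical Methods) gives the primary null: "The null hypothesis is that there is no difference in the margin exposure of the abutment between those 2 visits". The next sentence names the test: "Ho will be tested by means of Fisher's exact test, after each abutment margin is classified as it shows or not". The threshold is p below 5%. Section 3.2 puts the primary objective in the same terms, to "compare differences in margin exposure of the abutment between baseline to 6 months later". Neither section mentions the treatment arms in the primary comparison.

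The design is nevertheless a randomised two-arm one. Section 2 (Study Objectives) plans 24 patients and states: "The group will then be randomly split with half of the group receiving a custom abutment with margin placement .5mm sub-gingivally". The other half receive a margin 1.5 mm sub-gingivally.

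On timing, section 5.3 (Visit 3, surgery) says: "The dental implant will be covered with a cover screw to allow soft tissue healing". The abutment is delivered at Visit 5, week 8, where section 5.5 first schedules the outcome: "Research-driven data to include abutment exposure will be collected from subjects regarding fit of the provisional restoration". Exposure is recorded again at weeks 11 and 24. Section 5.7 describes the last visit: "Follow-up of crown restorations will be completed at 6 months post surgery (24 weeks").

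The secondary analyses in section 6.2 also use Fisher's test, for example for bleeding on probing: "Fisher's exact test will be used after the site has been evaluated for presence of bleeding or not". The groups being compared are not named there either.

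**The concern.** A null about two visits in one cohort calls for a test on paired binary data, driven by the subjects whose status changes. Fisher's exact test compares independent groups. The named test therefore does not test the stated null.

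The mismatch matters because it leaves the primary question open. Change over time, pooled over arms, and the difference between margin depths, which is the randomised contrast, are different questions, and one data set can be significant on one and not on the other. As written, the analyst could settle which was meant after seeing the results. The concern is this ambiguity, and not that the false-positive rate is inflated in general.

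The baseline visit is also undefined. No abutment is in place at surgery, so no margin exposure can be recorded then.

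**Working it through.** **Inputs.** 24 subjects split in half, so 12 per arm (section 2). Exposure is binary, the threshold is 5% (section 6.2) and is taken as two-sided. Exposure is assessed at weeks 8, 11 and 24 (sections 2 and 5.5 to 5.7). The documents give no exposure rates, within-subject correlation or dropout, and section 6.1 has no power calculation to reproduce. All rates below are assumptions, with all 24 subjects evaluable.

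**Step 1: which comparison do the Fisher tests fit?** Bleeding on probing is scheduled only at week 24, and provisional crown fit is judged once, at delivery. With one time point each, those Fisher tests make sense only between arms. This suggests a between-arm intention for the primary test too, but the primary null says otherwise.

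**Step 2: what is the interval?** Exposure is first recorded at week 8 and last at week 24. If week 8 is the baseline, the interval is 24 − 8 = 16 weeks. The six months in section 5.7 are counted from surgery.

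**Step 3: visit null, paired test v Fisher with visits treated as 24 v 24.** With no reversals and k newly exposed margins, the exact McNemar p-value is 2 × (1/2)^k.

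- 0/24 then 5/24. Fisher: 2 × C(24,5)/C(48,5) = 2 × 42,504/1,712,304 = 0.0496. Exact McNemar: 2 × (1/2)^5 = 0.0625. Mid-p McNemar: 0.0625 − (1/2)^5 = 0.031, so this disagreement depends on using the exact version.
- 6/24 then 12/24, no reversals. Fisher: 0.135. Exact McNemar: 2 × (1/2)^6 = 0.031.

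**Step 4: power on the visit null.** This is full enumeration of the paired 2×2 table at n=24, with no reversals. Exact McNemar then rejects when at least 6 margins are newly exposed.

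| Exposed at both visits | Newly exposed | Fisher, 24 v 24 | Exact McNemar |
|---|---|---|---|
| 20% | 30% | 48% | 77% |
| 5% | 20% | 35% | 34% |
| 0% | 20% | 54% | 34% |

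Neither test is always the more powerful.

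**Step 5: type I error of Fisher with visits as groups.** The grid has 10%, 20%, 30% or 50% exposed at each visit. At within-subject correlation 0 to 0.7 the error runs from 0.01% to 2.9%. Of the correlations tried, −0.3 to 0.7, it passes 5% only at −0.3 with 50% exposed (5.7%). Used this way, the test is mostly conservative.

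**Step 6: which null is meant can decide the result.**

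| Baseline | Week 24 | Visit null, exact McNemar | Between arms, Fisher 12 v 12 |
|---|---|---|---|
| 0/24 | 12/24, 6 per arm | 2 × (1/2)^12 = 0.0005 | 1.0 |
| 0/24 | 5/24, all in one arm | 2 × (1/2)^5 = 0.0625 | 2 × C(12,5)/C(24,5) = 2 × 792/42,504 = 0.037 |

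The two readings give opposite conclusions in both rows.

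**The case against.** The strongest reply is that the sponsor meant to compare the arms. The study is randomised, section 2 names abutment exposure at follow-up as the primary outcome, and the secondary Fisher tests fit only a between-arm comparison. On that reading the test is valid and the fault is a badly worded null. This is plausible, but it moves the error without removing it. The visit-to-visit wording appears in both 3.2 and 6.2, and neither mentions arms.

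A third reading is possible: change in exposure per subject, compared between arms. It coincides with week-24 exposure only if no margin shows at delivery, which the documents do not say. That adds to the ambiguity.

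It is also fair to say that the numerical examples are chosen and some are extreme. They show that the questions differ, not how likely this trial is to be affected. The 16-week interval holds only if week 8 is the baseline.

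Finally, this is a pilot in a convenience sample of 24 without a power basis, which limits the weight of any p-value. But section 6.2 sets a formal null and a 5% threshold, so the two should agree.

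**Conclusion.** The concern holds. On any of these readings, either the primary null or the primary test in section 6.2 is wrong as written, and the plan does not say which. This follows from the text and needs no assumed rates.

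The consequence can be a complete reversal: p=0.0005 v 1.0, or 0.0625 v 0.037, from the same data. Those figures assume 24 evaluable subjects, 12 per arm and no exposure at baseline. If Fisher's test were applied across visits, power could be lower or higher than with exact McNemar (48% v 77%; 54% v 34%), and type I error would be mostly conservative. Because this is the primary analysis, it must be corrected before outcome data are seen.

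**What to change.** Decide which question is primary and make null and test agree in section 6.2, before any outcome data are seen.

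1. **If change between visits is meant:** keep the null, name the baseline visit (exposure is first recorded at Visit 5, week 8), and use the exact McNemar test. Report the paired difference in proportions with a 95% CI, overall and by arm.
2. **If the randomised comparison is meant:** restate the null as no difference between the 0.5 mm and 1.5 mm arms in margin exposure at 24 weeks. Keep Fisher's exact test (12 v 12) and add a 95% CI for the difference. Make within-subject change a secondary paired analysis. If change per subject is to be compared between arms instead, say so and define it from a named baseline visit.

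In either case, state that the secondary Fisher tests compare the arms, and bring section 3.2 and the Statistical Methodology entry of the Study Summary into line.

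The cost is one decision and wording changes in three places. No new data, visits or patients are needed.
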